10.8 Sample size calculation

Phase Ib

Dose escalation: Cohorts of 3 to 6 evaluable patients will be enrolled in the dose escalation part including at least six patients at the MTD/RP2D level, as described in [Section 6.2.4](#).

Multiple cohorts may be sequentially enrolled to the same dose level. Additional cohorts of 1 to 6 patients may be enrolled at any dose level below the estimated MTD/RP2D for further elaboration of safety and PK parameters as required. At least 18 patients are expected to be treated in the dual-combination dose-escalation part of the study, for the model to have reasonable operating characteristics relating to its MTD recommendation (see [Appendix 5](#) for details). At least 12 patients are expected to be treated in the triple-combination dose-escalation part of the study.

Phase II

Arm 1 dual combination: Based on the prior distribution and decision rules described in [Section 10.4](#), it was explored how likely it is to wrongly declare activity given the true DCR = 20%, and how likely it is to correctly declare activity given the true DCR = 40%, when 28 patients are evaluated.

- If the true DCR = 20%, the probability to wrongly declare activity (i.e. seeing at least 9 patients with SD or better) is 9.0%.
- If the true DCR = 40%, the probability to correctly declare activity (i.e. seeing at least 9 patients with SD or better) is 85.2%.

If 9 out of 28 patients have at least SD or better, then the posterior risk of the true DCR being in the unacceptable category is 7.0%.

Note: if the interim analysis is performed, the probability to correctly declare activity if the true DCR = 40% is 82.3%.

Arm 2 dual combination: Based on the prior distribution and decision rules described in [Section 10.4](#), it was explored how likely it is to wrongly declare activity given the true ORR = 10%, and how likely it is to correctly declare activity given the true ORR = 20%, when 41 patients are evaluated:

- If the true ORR = 10%, the probability to wrongly declare activity (i.e. seeing at least 7 responses) is 11.0%.
- If the true ORR = 20%, the probability to correctly declare activity (i.e. seeing at least 7 responses) is 73.9%.

If 7 out of 41 patients have PR or CR, then the posterior risk of the true ORR being in the unacceptable category is 9.8%.

Arm 3 dual combination / Arm A triple combination: Based on the prior distribution and decision rules described in [Section 10.4](#), it was explored how likely it is to wrongly declare activity given the true ORR = 30%, and how likely it is to correctly declare activity given the true ORR = 50%, when 40 patients are evaluated:

- If the true ORR=30%, the probability of wrongly declaring at least moderate efficacy (i.e. at least 16 responses) is 11.5%.
- If the true ORR=50%, the probability of correctly declaring at least moderate efficacy (i.e. seeing at least 16 responses) is 92.3%.

If 16 out of 40 patients have PR or CR, then the posterior risk of the true ORR being in the unacceptable category is 9.0%.

11 Ethical considerations and administrative procedures

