Various dose pairs will be explored following the recommendation of an adaptive Bayesian logistic regression model (BLRM) for dose escalation with overdose control (EWOC) until the MTD is determined and/or until a consensus between the Sponsor and Investigators is reached and it is considered that there is no benefit of further increasing the dose. At least 6 patients eligible for the dose determining set (DDS) must be treated at the dose(s) declared to be the MTD/RP2D. At this time the RP2D, a dose less than or equal to the MTD, will be estimated based on a review of the totality of the available study data. Note: more than one combination and/or dosing schedule may be defined as MTD/RP2D. In the case that all dose combinations are considered to be too toxic by the BLRM after the first cohort, no MTD/RP2D can be defined.

Phase II

Following MTD/RP2D declaration, for the dual-combination patients will be enrolled in three Phase II arms. Phase II arm 1 will consist of 28 patients with non-resectable advanced BRAF V600 mutant metastatic colorectal cancer (mCRC) for whom no further effective standard therapy is available. An interim analysis for futility will be performed in arm 1 after 50% of the total number of patients in this arm have completed four cycles of treatment, to allow stopping early for futility when there is no treatment effect. The Phase II arm 2 will consist of 41 patients with locally advanced or metastatic BRAF V600 mutant melanoma who have progressed after

previous treatment with a selective BRAF inhibitor. The Phase II arm 3 will consist of 40 patients with locally advanced or metastatic BRAF V600 mutant melanoma who are naïve to previous treatment with a selective BRAF inhibitor. An interim analysis for futility will not be performed for arms 2 and 3, as signs of clinical activity have been reported for both MEK162 and LGX818 as single agent in patients with BRAF mutant melanoma patients (see [Section 1.2.1.2](#) and [Section 1.2.2.2.1](#)).

For the triple combination following MTD/RP2D declaration, 40 patients with locally advanced or metastatic BRAF V600 mutant melanoma who are naïve to previous treatment with a selective BRAF inhibitor will be enrolled in the Phase II arm A.

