10.7 Interim analysis

An interim analysis for futility will be performed in the phase II BRAF V600 mutant mCRC arm (dual-combination arm 1), when 14 patients (50% of the total sample size) have completed 4 cycles of treatment. As mentioned in Section 10.8, study results are successful if 9 responses are observed at the end of the trial. At the interim analysis, if the predictive probability of success is < 13%, i.e. if less than 3 responses (DCR at week 16) are observed, this study arm will be stopped for futility.

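### Arm 1 power with the futility interim is printed as 82.3%, but the stated rule gives 84.1% and the origin of 82.3% is not given

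*Protocol*

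**What the plan says.** Section 4.1 sets the size of the colorectal arm: "Phase II arm 1 will consist of 28 patients with non-resectable advanced BRAF V600 mutant" disease. Section 10.7 places the futility look "when 14 patients (50% of the total sample size) have completed 4 cycles of treatment", and defines the end-of-trial criterion: "study results are successful if 9 responses are observed at the end of the trial". The stopping rule is given in two forms joined as equivalent: "if the predictive probability of success is < 13%, i.e. if less than 3 responses (DCR at week 16) are observed".

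Section 10.8 then gives two operating characteristics of the 9-of-28 rule without the look: a false-positive rate of 9.0% when the DCR is truly 20%, and a power of 85.2% when it is truly 40%. A separate note says that, once the look is included, "the probability to correctly declare activity if the true DCR = 40% is 82.3"%. No method is given for this last figure.

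**The concern.** With a binary endpoint, a fixed look, a fixed stopping count and a fixed final cut-off, the power with the interim is an exact binomial sum. It needs no approximation and no unstated input. The printed value should therefore match to the decimal, as the other Phase II figures in section 10.8 do. It does not.

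It is also the only power figure the protocol gives for arm 1 with its planned interim included. A reader weighing the price of the look would take it from 85.2% and 82.3% as 2.9 points, more than twice what the stated rule costs.

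**Working it through.** **Inputs.** n = 28 (section 4.1); interim n1 = 14, stop if fewer than 3 with disease control, success at 9 or more (section 10.7); true DCR 20% and 40% (section 10.8); prior Beta(0.428, 1) (section 10.4.2.2).

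**Step 1: the figures without the interim.** With X ~ Bin(28, p):

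- P(X ≥ 9 | p = 0.2) = 0.0900; printed 9.0%.
- P(X ≥ 9 | p = 0.4) = 0.8515; printed 85.2%.
- Posterior risk at 9 of 28: P(DCR < 0.20) under Beta(9.428, 20) = 0.0700; printed 7.0%.

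All three match. The same calculations for arm 2 (7 of 41) give 11.0%, 73.9% and 9.8%, and for arms 3 and A (16 of 40) give 11.5%, 92.3% and 9.0%. These also match the printed values.

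**Step 2: do the two forms of the stopping rule agree?** The beta-binomial predictive probability of reaching 9 of 28 is 2.5% at 2 of 14 and 13.4% at 3 of 14. A threshold of 13% therefore means stopping at 2 or fewer. The two forms agree, so ambiguity in the rule does not explain the discrepancy.

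**Step 3: power with the interim at DCR 40%.**

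Power = Σ (x = 3 to 14) P(X1 = x) × P(X2 ≥ 9 − x), with X1 and X2 each Bin(14, 0.4).

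This equals the power without a look minus the successes lost by stopping:

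| x at interim | P(X1 = x) | P(X2 ≥ 9 − x) | Product |
|---|---|---|---|
| 0 | 0.00078 | 0.0583 | 0.00005 |
| 1 | 0.00731 | 0.1501 | 0.00110 |
| 2 | 0.03169 | 0.3075 | 0.00975 |
| Sum | 0.0398 | | 0.0109 |

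Power = 0.8515 − 0.0109 = 0.8406, or 84.1%. The printed value is 82.3%, a gap of 1.8 points.

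**Step 4: a bound that needs no full sum.** Only 4.0% of trials stop early at DCR 40%. Even at the best stopped count (2 of 14), the chance of later success is 31%. The loss therefore cannot exceed 0.0398 × 0.3075 = 0.0122, or 1.2 points. A loss of 2.9 points would need about 2.9 / 4.0, nearly three quarters, of the stopped trials to have succeeded otherwise.

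**Step 5: other stopping counts at 14 patients, success still at 9 of 28, DCR 40%.**

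| Stop if fewer than | Power |
|---|---|
| 1 | 85.2% |
| 2 | 85.0% |
| 3 (stated) | 84.1% |
| 4 | 79.7% |
| 5 | 68.6% |

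None gives 82.3%. Two shortcuts also miss: subtracting the stopping probability from 85.2% gives 81.2%, and multiplying 85.2% by one minus that probability gives 81.8%. With interim sizes from 8 to 21, the closest value is 82.5% (18 patients, stop below 5).

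**Step 6: false-positive rate with the interim.** The same sum at p = 0.2 gives 0.0867, or 8.7%, against 9.0% without the look. Early stopping occurs in 44.8% of trials at that rate.

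**The case against.** The strongest case against is materiality. A gap of 1.8 points would pass many rough tolerances for a power figure. It understates power, so nobody is led to think the design stronger than it is. Success is judged by a count, and nothing in the analysis uses 82.3%. Enrollment is closed (Appendix 10), so no planning decision remains to be changed. All of this stands, and it limits the point to a correction. It does not make the figure right: a tolerance suits approximate formulas or unstated inputs, whereas here the inputs are stated, the calculation is exact, and the neighbouring figures agree to the printed decimal.

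A second objection is that 82.3% may be a simulated value under the correct rule. Assuming 1,000 runs, the standard error is about 1.16 points, which puts 82.3% about 1.5 standard errors below 84.06%. That is possible. But the protocol mentions no simulation for Phase II; the 500-trial simulations in Appendix 5 concern the Phase Ib dose-escalation model, and 500 runs cannot yield exactly 82.3% (411.5 of 500). The objection supports asking for the method.

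Three stronger readings are tempting and are not supported:

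- A reader might infer that 82.3% belongs to a different design. The protocol shows only that the figure does not follow from the stated rule; where it came from is not given.
- A reader might take it as the power of arm 1 as it was run. Section 10.8 words it conditionally on the interim being performed, and the protocol plans the look without saying that it took place.
- A reader might count the absence of a false-positive rate with the interim as a defect. A futility-only stop can only lower that rate, so the printed 9.0% remains a valid upper bound.

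**Conclusion.** The point holds as a minor numerical error. Under the rule in sections 10.7 and 10.8, the probability of declaring activity at a true DCR of 40% with the interim is 84.1%, so the printed 82.3% understates it by 1.8 points. The price of the look is 1.1 points. The direction is conservative, and the sample size of 28, the cut-off of 9, the boundary of 3 of 14 and every decision built on them are unaffected.

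The result assumes independent patients with a common DCR, exactly 14 evaluated at the look and 28 at the end, and a binding stop below 3. The same independent-patient binomial model reproduces the figures without the interim.

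**What to change.** In section 10.8, arm 1, replace 82.3% by 84.1%. If 82.3% came from a different stopping rule or from simulation, state that rule, or the method and number of runs, beside the figure. Quoting 8.7% as the false-positive rate with the interim is optional. The cost is one number or one sentence; no design element or analysis changes.

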11.1 Regulatory and ethical compliance

This clinical study was designed, shall be implemented and reported in accordance with the ICH Harmonized Tripartite Guidelines for Good Clinical Practice, with applicable local regulations (including European Directive 2001/20/EC and US Code of Federal Regulations Title 21), and with the ethical principles laid down in the Declaration of Helsinki.

11.2 Responsibilities of the investigator and IRB/IEC/REB

The protocol and the proposed informed consent form must be reviewed and approved by a properly constituted Institutional Review Board/Independent Ethics Committee/Research Ethics Board (IRB/IEC/REB) before study start. A signed and dated statement that the protocol and informed consent have been approved by the IRB/IEC/REB must be given to the Sponsor before study initiation. Prior to study start, the investigator is required to sign a protocol signature page confirming his/her agreement to conduct the study in accordance with these documents and all of the instructions and procedures found in this protocol and to give access to all relevant data and records to the Sponsor's monitors, auditors, Sponsor Clinical Quality Assurance representatives, designated agents of the Sponsor, IRBs/IECs/REBs and regulatory authorities as required.

11.3 Informed consent procedures

Eligible patients may only be included in the study after providing written (witnessed, where required by law or regulation), IRB/IEC/REB-approved informed consent or, if incapable of doing so, after such consent has been provided by a legally acceptable representative of the patient. In cases where the patient's representative gives consent, the patient should be informed about the study to the extent possible given his/her understanding. If the patient is capable of doing so, he/she should indicate assent by personally signing and dating the written informed consent document or a separate assent form. Informed consent must be obtained before conducting any study-specific procedures (i.e. all of the procedures described in the protocol). The process of obtaining informed consent should be documented in the patient source documents. The date when a subject's Informed Consent was actually obtained will be captured in their eCRFs.

The Sponsor will provide investigators in a separate document with a proposed informed consent form (ICF) that is considered appropriate for this study and complies with the ICH GCP guideline and regulatory requirements. Any changes to this ICF suggested by the investigator must be agreed to by the Sponsor before submission to the IRB/IEC/REB, and a copy of the approved version must be provided to the Sponsor's monitor after IRB/IEC/REB approval.

Women of child bearing potential should be informed that taking the study medication may involve unknown risks to the fetus if pregnancy were to occur during the study and agree that in order to participate in the study they must adhere to the contraception requirement for the duration of the study. If there is any question that the patient will not reliably comply, they should not be entered in the study.

For this study, the following ICFs apply:

- Molecular pre-screening consent form (if applicable)
- Study consent form; one for dual study treatment combination and one for triple study treatment combination [the ICF for triple study treatment combination (LGX818 / MEK162 / LEE011) is not applicable for the USA and Singapore].

11.4 Discontinuation of the study

The Sponsor reserves the right to discontinue this study under the conditions specified in the clinical study agreement. Specific conditions for terminating the study are outlined in [Section 4.4](#).

11.5 Publication of study protocol and results

The Sponsor assures that the key design elements of this protocol will be posted in a publicly accessible database such as clinicaltrials.gov. In addition, upon study completion and finalization of the study report the results of this study will be either submitted for publication and/or posted in a publicly accessible database of clinical study results.

11.6 Data Sharing

Pfizer provides researchers secure access to patient-level data or full CSRs for the purposes of “bonafide scientific research” that contributes to the scientific understanding of the disease, target, or compound class. Pfizer will make available data from these trials 24 months after study completion. Patient-level data will be anonymized in accordance with applicable privacy laws and regulations. CSRs will have personally identifiable information redacted.

Data requests are considered from qualified researchers with the appropriate competencies to perform the proposed analyses. Research teams must include a biostatistician. Data will not be provided to applicants with significant conflicts of interest, including individuals requesting access for commercial/competitive or legal purposes.

11.7 Study documentation, record keeping and retention of documents

Each participating site will maintain appropriate medical and research records for this trial, in compliance with Section 4.9 of the ICH E6 GCP, and regulatory and institutional requirements for the protection of confidentiality of subjects. As part of participating in an Array BioPharma-sponsored study, each site will permit authorized representatives of the sponsor(s) and regulatory agencies to examine (and when required by applicable law, to copy) clinical records for the purposes of quality assurance reviews, audits and evaluation of the study safety and progress.

Source data are all information, original records of clinical findings, observations, or other activities in a clinical trial necessary for the reconstruction and evaluation of the trial. Examples of these original documents and data records include, but are not limited to, hospital records, clinical and office charts, laboratory notes, memoranda, subjects’ diaries or evaluation checklists, pharmacy dispensing records, recorded data from automated instruments, copies or transcriptions certified after verification as being accurate and complete, microfiches, photographic negatives, microfilm or magnetic media, x-rays, and subject files and records kept

at the pharmacy, at the laboratories, and medico-technical departments involved in the clinical trial.

Data collection is the responsibility of the clinical trial staff at the site under the supervision of the site Principal Investigator. The study case report form (CRF) is the primary data collection instrument for the study. The investigator should ensure the accuracy, completeness, legibility, and timeliness of the data reported in the CRFs and all other required reports. Data reported on the CRF, that are derived from source documents, should be consistent with the source documents or the discrepancies should be explained. All data requested on the CRF must be recorded. Any missing data must be explained. Any change or correction to a paper CRF should be dated, initialed, and explained (if necessary) and should not obscure the original entry. For electronic CRFs an audit trail will be maintained by the system. The investigator should retain records of the changes and corrections to paper CRFs.

The investigator/institution should maintain the trial documents as specified in Essential Documents for the Conduct of a Clinical Trial (ICH E6 Section 8) and as required by applicable regulations and/or guidelines. The investigator/institution should take measures to prevent accidental or premature destruction of these documents.

Essential documents (written and electronic) should be retained for a period of not less than fifteen (15) years from the completion of the Clinical Trial unless Sponsor provides written permission to dispose of them or, requires their retention for an additional period of time because of applicable laws, regulations and/or guidelines

11.8 Confidentiality of study documents and patient records

The investigator must ensure anonymity of the patients; patients must not be identified by names in any documents submitted to the Sponsor. Signed informed consent forms and patient enrollment log must be kept strictly confidential to enable patient identification at the site.

11.9 Audits and inspections

Source data/documents must be available to inspections by the Sponsor or designee or Health Authorities.

11.10 Financial disclosures

Financial disclosures should be provided by study personnel who is directly involved in the treatment or evaluation of patients at the site - prior to study start.

12 Protocol adherence

Investigators ascertain they will apply due diligence to avoid protocol deviations. Under no circumstances should the investigator contact the Sponsor or its agents, if any, monitoring the study to request approval of a protocol deviation, as no authorized deviations are permitted. If the investigator feels a protocol deviation would improve the conduct of the study this must be considered a protocol amendment, and unless such an amendment is agreed upon by the Sponsor and approved by the IRB/IEC/REB it cannot be implemented. All significant protocol deviations will be recorded and reported in the CSR.

14.1.1 Introduction

The purpose of this document is to provide the working definitions and rules necessary for a consistent and efficient analysis of efficacy for oncology studies in solid tumors. This document is based on the RECIST criteria for tumor responses ([Therasse 2000](#)) and the revised RECIST guidelines (version 1.1) ([Eisenhauer 2009](#)).

This document will not address the use of RECIST 1.1 for glioblastoma multiforme (GBM).

The efficacy assessments described in Section 14.1.2 and the definition of best response in [Section 14.1.17](#) are based on the RECIST 1.1 criteria but also give more detailed instructions and rules for determination of best response. [Section 14.1.18](#) is summarizing the “time to event” variables and rules which are mainly derived from internal discussions and regulatory consultations, as the RECIST criteria do not define these variables in detail. [Section 14.1.28](#) of this guideline describes data handling and programming rules. This section is to be referred to in the analysis plan(s) to provide further details needed for programming.

14.1.2 Efficacy assessments

Tumor evaluations are made based on RECIST criteria for tumor responses ([Therasse 2000](#)) and the revised RECIST guidelines (version 1.1) ([Eisenhauer 2009](#)).

The assessment schedule for tumor assessments is described in [Section 7.2.1](#) of the protocol. Frequency of tumor re-evaluation while on treatment should be adapted to the type and schedule of treatment, and the type of tumor treated.

It is assumed that all information which is considered for assessment of the tumor is captured in the RECIST eCRF, i.e. not merged from several sources.

14.1.3 Definitions

14.1.4 Disease measurability

In order to evaluate tumors throughout a study definitions of measurability are required in order to classify lesions appropriately at baseline. In defining measurability a distinction also needs to be made between nodal lesions (pathological lymph nodes) and non-nodal lesions.

- **Measurable disease** - the presence of at least one measurable nodal or non-nodal lesion. If the measurable disease is restricted to a solitary lesion, its neoplastic nature should be confirmed by cytology/histology.

For patients without measurable disease see [Section 14.1.26](#).

Measurable lesions (both nodal and non-nodal)

- Measurable non-nodal - As a rule of thumb, the minimum size of a measurable non-nodal target lesion at baseline should be no less than double the slice thickness or 10mm whichever is greater - e.g. the minimum non-nodal lesion size for CT/MRI with 5mm cuts will be 10 mm, for 8 mm contiguous cuts the minimum size will be 16 mm.
- Lytic bone lesions or mixed lytic-blastic lesions with identifiable soft tissue components, that can be evaluated by CT/MRI, can be considered as measurable lesions.
- Measurable nodal lesions (i.e. lymph nodes) - Lymph nodes ≥ 15 mm in short axis can be considered for selection as target lesions. Lymph nodes measuring ≥ 10 mm and < 15 mm are considered non-measurable. Lymph nodes smaller than 10 mm in short axis at baseline, regardless of the slice thickness, are normal and not considered indicative of disease.
- Non-measurable lesions - all other lesions are considered non-measurable, including small lesions (longest diameter < 10 mm with CT scan or pathological lymph nodes with ≥ 10 to < 15 mm short axis), e.g., blastic bone lesions, leptomeningeal disease, ascites, pleural/pericardial effusion, inflammatory breast disease, lymphangitis cutis/pulmonis, abdominal masses that are not confirmed and followed by imaging techniques, and cystic lesions.

If any lesion should be handled differently, this must be clearly stated and justified in the protocol, e.g. tumor lesions that are situated in a previously irradiated area might or might not be considered measurable, and the conditions under which such lesions should be considered must be defined in the protocol when appropriate.

